To identify potential treatment moderators and further understand current health services for smoking cessation among Veterans, it is essential to determine existing health disparities in cessation treatment among VHA patients with a variety of chronic care conditions.

For this study aim, the data source will be a data request from Corporate Data Warehouse (CDW). We will create two complimentary datasets. First, we will investigate predictors of tobacco cessation pharmacotherapy fills among a cohort of Veteran tobacco users (FY 2018). Second, we will investigate overall rates of tobacco cessation pharmacotherapy fills over time (2011 to present).

Pharmacotherapy Disparities among a Cohort of Tobacco Users

Veteran health data, which may include PHI (e.g., dates of care and patient address), will be gathered starting from FY18 (pre-pandemic). After requesting data access via the Data Access Request Tracker (DART), Veterans who have positive tobacco use health factors will be identified from VA's Regional and/or Corporate Data Warehouse. During the retrospective observation period, tobacco use will be determined based on a validated algorithm for identifying smoking status from the EMR (Calhoun et al., 2017; McGinnis et al., 2011). Data will be extracted on tobacco use health factors, pharmacy records of medications dispensed, primary care/ID clinic outpatient healthcare encounters, pain intensity vital sign data, history of positive homelessness screening, history of positive food insecurity screening, patient demographics (race, ethnicity, service-connected disability, birth sex, gender identity, county, address), and diagnosis codes for comorbid disorders of interest (including but not limited to HIV, Hepatitis C coinfection, cardiovascular disease, cancer, and psychiatric disorders). Number of clinic visits attended in the 12-month period prior to the positive health factor will be collected as a control variable. Patient county and address will be used to extract data on neighborhood deprivation (Bhavsar et al., 2018) and economic inequality (GINI; Bee, 2012).

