The population of tobacco users will be determined by fiscal year using health factors. For each fiscal year, the pharmacotherapy prescription rate will be calculated for each type of pharmacotherapy by dividing the total number of Veterans receiving a prescription for tobacco cessation pharmacotherapy by the total number of Veterans who meet criteria for current tobacco use.

We will examine trends over time, as well as systems-level determinants, including geographical region, facility-level proportion of Veteran patients who live rurally (extracted by year and by facility from the Rural Veterans Health Care Atlas), and state-level tobacco use prevalence.

AIM 3 METHODS – SUCCESSIVE COHORT DESIGN FOR TREATMENT REFINEMENT

We will use a successive cohort design to integrate and user-test the proposed intervention. The successive cohort design is an iterative process that is designed to refine behavioral treatments in the initial development stage (Epstein et al., 2007). This design involves multiple steps of development: 1) identifying theoretically-supported treatment models; 2) identifying key intervention elements; 3) developing preliminary intervention materials; and 4) revising the intervention iteratively based upon qualitative and quantitative data collected during successive patient cohorts. See below for proposed preliminary intervention methodology, as well as methodology for iteratively revising the intervention based upon patient qualitative feedback.

SAMPLE RECRUITMENT

A total of 3 cohorts of 5 patients each ($N = 15$) will complete the intervention and provide feedback after the treatment phase is complete. Participants will be recruited from the Durham VAHCS. Inclusion criteria are: VHA patient, HIV positive serostatus, currently smoking ≥ 7 cigarettes per week, and willing to complete study procedures. Exclusion criteria are: current hospitalization, acute risk for suicide documented in the medical record, or inability to complete study procedures.

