Quantitative Analysis. Regarding quantitative data received from Duke, data from veterans who smoke, people living with HIV who smoke, and members of the general public who smoke will be analyzed separately. First, data will be cleaned. Participants will be excluded from analysis if they meet any of the following criteria: greater than 2 endorsed bogus items, self-reported “very little” or “no” effort or attention, or a “no” response to the question “In your honest opinion, should we use your data in our analyses in this study?” After data cleaning, the following descriptive statistics will be calculated for satisfaction ratings on each SmokefreeVET message: range, mean, and standard deviation. Items falling below an 8 on mean satisfaction will be reviewed by the study staff in the context of qualitative findings to make final decisions regarding their inclusion in the final relapse-prevention message library.

Aim 2:

In order to examine disparities in healthcare delivery of smoking cessation prescriptions, we will use a longitudinal retrospective design. Generalized linear mixed modeling (GLMM) with a logit link and binomial variance will be used to determine differences by variables of interest in likelihood of pharmacotherapy dispensation following positive tobacco health factors screening. GLMMs appropriately accommodate multi-level data structures with unbalanced design for analyzing repeated observations across multiple individuals nested within clinics. Clinic- and person-level random effects will be included in statistical models to account for correlation among patients within the same clinic and repeated measurements on the same individual over time, respectively. Covariates will be assessed for collinearity before entering them simultaneously into the GLMM.

Aim 3:

Tobacco Cessation Treatment Preferences among Veteran Smokers

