We will use rapid qualitative analytic methods to analyze participant feedback from post-treatment qualitative interviews (Watkins, 2017). For each study cohort of 5 participants, study staff will complete written summaries of interview audio recordings, and will enter these summaries into a study database. Interview summaries across participants will be displayed by their structural content (i.e., intervention strength, intervention weaknesses, and areas for improvement). Then, thematic analysis will be used to code emergent themes and patterns within each content area. Given the sample size for this successive cohort study ($N = 15$), it is estimated that we will identify and be able to address 97% of usability problems in the treatment personalization program (Faulkner, 2003).

Aim 4:

Analysis and interpretation will focus on describing the acceptability of the intervention and the feasibility of the trial approach. Given power limitations of using a small sample in a two-group study, it is not appropriate to perform any efficacy analyses. Regarding feasibility, we will describe patient recruitment, treatment retention, the proportion of patients who withdraw after randomization, and the proportion of patients who withdraw from treatment. In order to ascertain acceptability of the intervention, we will describe patient satisfaction, therapist satisfaction, and app utilization metrics. We will describe the proportion of patients that quit in each arm (but will not test group differences in abstinence).

References

Bee, A. (2012). *Household income inequality within US counties: 2006-2010*. US Department of Commerce, Economics and Statistics Administration, US Census Bureau.

Benowitz, N. L., & Prochaska, J. J. (2013). Smoking cessation after acute myocardial infarction. *Journal of the American College of Cardiology*, 5, 533-535.

Bhavsar, N. A., Gao, A., Phelan, M., Pagidipati, N. J., & Goldstein, B. A. (2018). Value of neighborhood socioeconomic status in predicting risk of outcomes in studies that use electronic health record data. *JAMA network open*, 1(5), e182716-e182716.

Braithwaite, R. S., Fang, Y. X., Tate, J., Mentor, S. M., Bryant, K. J., Fiellin, D. A., & Justice, A. C. (2016). Do alcohol misuse, smoking, and depression vary concordantly or sequentially? A longitudinal study of HIV-infected and matched uninfected veterans in care. *Aids and Behavior*, 20(3), 566-572. doi:10.1007/s10461-015-1117-8

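### The Aim 2 FY18 cohort model has no random effect or clustered variance at the area level, so standard errors for neighborhood deprivation and the Gini are too small if outcomes correlate within areas after the clinic effect

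*Combined protocol and SAP*

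**What the plan says.** DATA ANALYSES, Aim 2, gives one model: "Generalized linear mixed modeling (GLMM) with a logit link and binomial variance will be used to determine differences by variables of interest". It describes the data as "repeated observations across multiple individuals nested within clinics" and sets the random structure: "Clinic- and person-level random effects will be included in statistical models to account for correlation among patients within the same clinic". The person effect covers repeated measurements on one individual. All predictors go in together: "Covariates will be assessed for collinearity before entering them simultaneously into the GLMM". No area-level effect and no cluster-robust variance is mentioned.

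The predictors are listed under AIM 2 METHODS, Pharmacotherapy Disparities among a Cohort of Tobacco Users. They include two variables defined by where the Veteran lives: "Patient county and address will be used to extract data on neighborhood deprivation", and, from the same source, economic inequality measured by the Gini. The reference cited for the Gini is titled "Household income inequality within US counties: 2006-2010". The section itself calls this variable a neighborhood measure, and it does not state the area unit for either variable.

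The second Aim 2 dataset has its own section, Pharmacotherapy Prescriptions Over Time. There the outcome is an aggregate: "For each fiscal year, the pharmacotherapy prescription rate will be calculated for each type of pharmacotherapy". The section then proposes to examine "systems-level determinants, including geographical region, facility-level proportion of Veteran patients who live rurally", and state-level tobacco use prevalence. No model is given for this dataset.

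**The concern.** A variable with one value per county carries about as much information as there are counties, not as there are Veterans. The model must know that residents of one county may resemble each other for reasons other than the covariate. A clinic effect does this only in part. It removes differences between clinics, but counties within one clinic's catchment can still differ, and residents of one county can attend different clinics. Counties are then crossed with clinics rather than nested in them. Person effects do not help, because they are independent from one resident to the next.

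Finding disparities is the stated purpose of Aim 2, and social determinants are among its named predictors. If their intervals are too narrow, chance differences between areas could be read as disparities. The plan already accepts that clustering must be modeled. It leaves out the level at which these covariates vary.

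**Working it through.** **There is no plan figure to reproduce.** Aim 2 states no sample size, alpha, prescribing rate, intraclass correlation or number of patients per area.

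**Assumed inputs (none from the documents).** Prescribing rate p = 0.23; two-sided 5% test; one observation per Veteran; m patients per county, equal across counties; s = SD of county effects on the log-odds scale that remains after the clinic effect.

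**Formula.** The sampling variance of one county's log-odds is about 1/[m·p(1−p)]. A model without a county term counts only this. The true variance adds s². The ratio of true to counted variance is

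VIF = 1 + m·p(1−p)·s², with p(1−p) = 0.23 × 0.77 = 0.1771.

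The reported standard error is too small by a factor of √VIF, and a nominal 5% test rejects with probability 2·[1 − Φ(1.96/√VIF)].

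Example, s = 0.15 and m = 300: VIF = 1 + 300 × 0.1771 × 0.0225 = 2.195; √VIF = 1.48; 1.96/1.48 = 1.32; rejection 19%.

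| s | m | VIF | SE too small by factor | True rejection at nominal 5% |
|---|---|---|---|---|
| 0 | any | 1.00 | 1.00 | 5.0% |
| 0.05 | 100 | 1.04 | 1.02 | 5.5% |
| 0.05 | 300 | 1.13 | 1.06 | 6.6% |
| 0.10 | 300 | 1.53 | 1.24 | 11% |
| 0.15 | 5 | 1.02 | 1.01 | 5.2% |
| 0.15 | 10 | 1.04 | 1.02 | 5.5% |
| 0.15 | 100 | 1.40 | 1.18 | 10% |
| 0.15 | 300 | 2.20 | 1.48 | 19% |
| 0.15 | 1000 | 4.98 | 2.23 | 38% |

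**Sensitivity to p.** With p = 0.10, s = 0.15 and m = 300: VIF = 1 + 300 × 0.09 × 0.0225 = 1.61, rejection 12%.

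**Check by simulation.** The set-up was 130 clinics, 10 counties per clinic, 20% of each county's patients using a second clinic, clinic effects fitted, and 600 replicates. With s = 0.15, rejection was 9.8%, 16.5% and 36.8% for m = 100, 300 and 1000. With s = 0 it was 3.7%, 5.0% and 4.7%. Fitting clinic effects did not remove the inflation.

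**Second parameterization.** Using 1 + (n − 1)·ICC, with n patients per area and the ICC left after the clinic effect:

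- 5 per area, ICC 0.02: 1.08, rejection 5.9%.
- 100 per area, ICC 0.001: 1.10, rejection 6.2%.
- 100 per area, ICC 0.01: 1.99, rejection 16.5%.

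The pattern is the same: negligible for small areas, material for populous ones with residual correlation.

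**Trend dataset.** No arithmetic applies. The rate is defined as Veterans prescribed over Veterans using tobacco, per fiscal year and per type of drug. Taken literally, that is one number per year and type, from which no facility or state coefficient can be estimated. The same section takes rurality by year and by facility, so facility-by-year rates are the natural intention, but the text does not say so.

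**The case against.** The strongest reply is that the size is unknown. Every input above is assumed. A residual county SD of 0.05 at 100 to 300 patients per county moves a 5% test only to between 5.5% and 6.6%. The clinic effect will absorb part of any geographic correlation. If deprivation is measured for small areas, the issue nearly vanishes, and the county level of the Gini is inferred from the title of a reference. Aim 2 is also a retrospective observational analysis, and the randomized pilot in Aim 4, which is descriptive, is untouched. All of this stands. It makes the point conditional but does not remove it, because the plan offers no safeguard if the correlation is there.

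Three stronger readings are tempting and are not supported.

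- A reader might infer that facility rurality and state tobacco prevalence are tested in the clinic-and-person model. They are named only for the trend dataset, and DATA ANALYSES does not say that its model is used there. That gap is an unstated model, not a model with wrong standard errors. If clinic means facility, a term undefined in the plan, the clinic effect would already sit at the level of a facility covariate.
- A reader might conclude that false determinants will be declared. That needs residual area variance, which no document gives, and a decision rule, which the plan does not state.
- A reader might infer from the reference title that 2006-2010 Gini values will be attached to an FY18 cohort. The plan cites the report beside the Gini but does not say which years' values will be used.

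**Conclusion.** The point holds in conditional form. The FY18 cohort model includes area-valued predictors and makes no provision for correlation within areas beyond clinic. If such correlation exists, the standard errors of the deprivation and Gini coefficients are understated. Over the assumed county values in the table, the true rejection rate of a nominal 5% test runs from 5% with no residual variance to 38% with SD 0.15 and 1000 patients per county. The remedy is inexpensive and better matched to the question, so it is worth making as an improvement to the plan. The trend dataset is a secondary matter of incomplete specification.

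**What to change.** In DATA ANALYSES, Aim 2:

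1. State the area unit at which deprivation and the Gini are each measured.
2. Keep the clinic and person effects, and add a random effect crossed with clinic at that unit: county for a county Gini, and the census area for deprivation if those areas hold many patients. Alternatively, use variance clustered at that level.
3. Define clinic in relation to facility.
4. For the trend dataset, state that rates are computed by facility and fiscal year, and model them with facility and state effects.

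The cost is plan wording, longer model run time, and wider intervals for the area-level coefficients where area correlation is present. If there is none, little is lost. No new data collection is needed, because county and address are already to be extracted.
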